5.2 Enhanced Recovery Strategy for Tolerance of Solid Food

Poor tolerance of solid food is proportional to severity in patients with AP, identified through an international Delphi process and validated in a study of 439 patients to be second to organ failure in the assessment of AP severity (Buxbaum 2018). Furthermore, as the Phase 2a study CM4620-201 showed a marked improvement in tolerance of solid food in association with CM4620 administration compared to placebo, this parameter will be measured as the primary efficacy endpoint. Patients randomized into the study will be offered a low fat, ≥500-calorie solid meal at each mealtime after the infusion of the first dose of study drug if alert and not on mechanical ventilation or if not NPO for a planned surgery/medical procedure, or if not NPO because of an acute medical condition. If the patient does not wish to eat the solid meal when offered or is unable to tolerate the solid meal, they should then be offered a liquid meal. The same approach should occur at each subsequent mealtime until discharge. When patients eat a solid meal, it should be recorded if they ate ≥50% of the meal and if they either vomited or experienced an increase in abdominal pain in the two hours after the meal. Tolerating solid food is defined by the consumption of \geq 50% of a low fat, \geq 500-calorie solid meal without an increase in abdominal pain or vomiting in the two hours after the meal. The time when the patient receives a solid meal that is then tolerated shall be recorded. If the patient is not tolerating either solid or liquid meals, tube feedings should be considered as per the AGA Institute Guideline on Initial Management of Acute Pancreatitis.

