8.3 Randomization Using IXRS System

8.4 Start of First Infusion of Study Drug (SFISD)

The SFISD should begin within 8 hours of the patient or LAR providing informed consent.

Perform the following procedures immediately prior to the SFISD:

- Record concomitant medications
- Infuse the first dose of study drug
 - Record the time of the SFISD
 - o Record the time when the infusion is finished
 - Draw blood sample for PK as soon as possible after completion of the first infusion of study drug (within +2 hours)
- Begin Enhanced Recovery Strategy for Tolerance of Solid Food (see Section 5.2) and continue daily until patient discharge.

8.5 24 hours

24 hours from the SFISD:

- Record concomitant medications
- Record vital signs closest to the scheduled time of assessment
- Record the patient's pain using the PNRS closest to the scheduled time of assessment
- Record SpO₂ and the FiO₂ (see Section 8.12.6) closest to the scheduled time of assessment
- Determine if, and when the patient tolerated solid food in the previous 24 hours (see Section 5.2)
- Determine if the patient met the medically indicated discharge criteria in the previous 24 hours (see Section 5.3)
- Perform AE/SAE assessment
- Prior to the infusion of the second dose of study drug:
 - Draw blood samples for CBC, differential, platelets, Serum Procalcitonin and Serum Chemistries - analyze at local lab. Testing may be performed on blood drawn in the previous 12 hours.
 - Draw blood sample for Serum IL-6 send to central lab. Testing may be performed on blood drawn in the previous 12 hours.
 - O Draw blood sample for PK prior to the infusion of the second dose of study drug (within -30 min) send to central lab.
 - Obtain urine sample for Urine NGAL-send to central lab. Testing may be performed on urine collected in the previous 12 hours.
- Start the infusion of second dose of study drug 24 hours (±1 hour) from the SFISD (see Section 5.3)
 - o Record the time when the infusion starts and finishes

8.6 48 hours

48 hours from the SFISD:

- Record concomitant medications
- Record vital signs closest to the scheduled time of assessment
- Record the patient's pain using the PNRS closest to the scheduled time of assessment
- Record SpO₂ and the FiO₂ (see Section 8.12.6) closest to the scheduled time of assessment
- Determine if, and when the patient tolerated solid food in the previous 24 hours (see Section 5.2)

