10.7 Efficacy Analysis

The efficacy endpoints are the following:

Primary endpoint

Time to solid food tolerance

Secondary endpoints

- Solid food tolerance at 48 hours, 72 hours, and 96 hours after the SFISD and at discharge
- Time to medically indicated discharge
- Length of stay in the hospital
- Length of stay in the ICU for patients admitted to the ICU
- Re-hospitalization for AP by Day 30
- Change in severity of AP by CTSI score from screening to Day 30
- Development of pancreatic necrosis ≥30% and >50%
- The persistence of SIRS ≥48 hours after the SFISD
- Incidence, severity, and duration of organ failure
- Mortality by Day 30
- Change in pain score and opioid use

Exploratory endpoints

- Development of infected pancreatic necrosis
- Development of sepsis
- Hospital procedures for the management of pancreatic necrosis
- Change in GCSI-DD score
- Change in albumin
- Change in ANC/ALC ratio and IL-6 levels
- Change in urine NGAL

Time to solid food tolerance is the number of hours from the date and time of the SFISD for the patient to the first date and time the patient receives a solid meal that is tolerated, which is defined as eating \geq 50% of a low fat, \geq 500-calorie solid meal without an increase in abdominal pain or vomiting in the two hours after completing the meal.

Time to solid food tolerance for patients who could not tolerate solid food during the study will be censored on the latest date and time of food tolerance assessment.

Time-to-event endpoints will be summarized using Kaplan-Meier analyses. The medians and quartiles of time-to-events will be summarized. Time to solid food tolerance will be compared between each treatment groups and the placebo group using the stratified log-rank test as the primary analysis. The tests will be at an alpha level of 0.05 without multiplicity adjustment. The stratification variables will include gender (male vs. female) and disease severity status (higher

risk for organ failure defined by the presence of both a HCT \geq 44% for men, or \geq 40% for women, and a PaO₂/FiO₂ \leq 360 before randomization (Figure 4).

In addition, the hazard ratio (HR) and the 95% CI will be estimated using a Cox proportional-hazard model with treatment group as the independent variable and stratified by the same randomization stratification factors as used for the log-rank test.

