- b. The most extreme value for each criterion in the 24 hours before consent or following consent but prior to randomization may be used.
- ^{c.} A CECT already performed in the 24 hours prior to the patient or LAR providing informed consent may be used as the Screening CECT. In addition to the Screening and the Day 30 visit CECTs, CECTs performed as standard of care after randomization and to 25 days after SFISD will be captured and submitted for central reading. If the CECT is performed 25 to 29 days after SFISD, it will substitute for the Day 30 visit CECT scan and will be captured.
- d. Hematocrit collected as standard of care within 12 hours of consent or following consent but prior to randomization may be used for Inclusion Criterion 3c.
- e. Biomarker blood and urine samples and blood samples for PK will be analyzed at central laboratory. If site or patient does not participate in these assessments this will be documented at start of study and will not be considered a protocol deviation.
- f. Determine if patient had met the medically indicated discharge criteria within the prior 24- or 48-hour visit assessment.
- Patients will be offered a low fat, ≥500-calorie solid meal at each mealtime after the infusion of the first dose of study drug until discharge if alert and not on mechanical ventilation, or if not NPO for a planned surgery/medical procedure, or if not NPO because of an acute medical condition. If the patient does not wish to eat the solid meal when offered or is unable to tolerate the solid meal, they should then be offered a liquid meal. Determine for each meal if the patient ate ≥50% of the meal without vomiting or having abdominal pain in the two hours after the meal.
- h. The mGCSI-DD score will be completed by all eligible patients at the baseline assessment and on the day of discharge, which will vary by patient as shown in schedule above. In addition, if the patient remains hospitalized at 96 and/or 168 hours and/or at Day 14 and/or Day 21 patient should be requested to record their symptoms at bedtime using the mGCSI-DD worksheet. Patients will be trained on completing the mGCSI-DD worksheet. Upon discharge, patient will record the mGCSI-DD score daily before bedtime until the Day 30 visit.

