- a. Blood sample for serum pregnancy test, serum lipase and CBC+diff+Platelets at Screening will be analyzed at local laboratory. May use results obtained as standard of care if blood drawn in the previous 12 hours prior to consent or following consent but prior to randomization. Following screening, all protocol-required blood samples, except as noted in Footnote "e", will be analyzed at local laboratory. Baseline blood samples including biomarkers may be performed on blood drawn in the previous 12 hours of randomization. For all later assessment times, blood drawn in the previous 12 hours maybe used (except PK).
- b. The most extreme value for each criterion in the 24 hours before consent or following consent but prior to randomization may be used.
- c. A CECT already performed in the 24 hours prior to the patient or LAR providing informed consent may be used as the Screening CECT. In addition to the Screening and the Day 30 visit CECTs, CECTs performed as standard of care after randomization and to 25 days after SFISD will be captured and submitted for central reading. If the CECT is performed 25 to 29 days after SFISD, it will substitute for the Day 30 visit CECT scan and will be captured.
- d. Hematocrit collected as standard of care within 12 hours of consent or following consent but prior to randomization may be used for Inclusion Criterion 3c.
- e. Biomarker blood and urine samples and blood samples for PK will be analyzed at central laboratory. If site or patient does not participate in these assessments this will be documented at start of study and will not be considered a protocol deviation.
- f. Determine if patient had met the medically indicated discharge criteria within the prior 24- or 48-hour visit assessment.
- g. Patients will be offered a low fat, ≥500-calorie solid meal at each mealtime after the infusion of the first dose of study drug until discharge if alert and not on mechanical ventilation, or if not NPO for a planned surgery/medical procedure, or if not NPO because of an a cute medical condition. If the patient does not wish to eat the solid meal when offered or is unable to tolerate the solid meal, they should then be offered a liquid meal. Determine for each meal if the patient ate ≥50% of the meal without vomiting or having abdominal pain in the two hours after the meal

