8.6.3 Main Analytical Approach

Time to solid food tolerance through Day 30 visit will be analyzed based on the Generalized Multiple Comparison Modelling (gMCP-Mod) approach described in Session 8.6.1.

Time to solid food tolerance is defined as the number of hours from the date and time of the SFISD for the patient to the first date and time the patient receives a solid meal that is tolerated. If the mealtime was not recorded, the mealtime will be estimated using the middle time of the meal serving interval.

Tolerating a solid meal is defined as eating \geq 50% of a low fat, \geq 500-calorie solid meal without an increase in abdominal pain or vomiting within the two hours of mealtime. In addition, to meet the definition, all subsequent meals during the hospitalization should not show an increase in abdominal pain or vomiting within the two hours of mealtime. If a procedure that could impact food tolerance is performed after a solid meal is initially tolerated that results in subsequent meals not being tolerated, the time of the initial tolerated meal will be considered in the calculation of the time to solid food tolerance. The procedures that impact food tolerance and/or its assessment are defined as (1) a procedure that requires a period of nil by mouth (2) a procedure and/or treatment that causes gastrointestinal dysfunction e.g., cholecystectomy, necrosectomy. The procedures performed after the initial food tolerance will be reviewed before the database lock to identify the procedures that could impact the time to the tolerated solid food. If the subject was not discharged from the hospital during the study and did not tolerate solid food, the time to solid food tolerance will be censored at the latest date and time of the hospital stay.

If a patient is discharged home without tolerating solid food, the daily record of the modified American Neurogastroenterology and Motility Society Gastrointestinal Cardinal Symptom Index Daily Diary (mGCSI-DD) at or after hospital discharge will be used in the calculation of the time to solid food tolerance. The patients who did not tolerate solid food while hospitalized will be considered as tolerating solid food at or after hospital discharge at 8am on the first of three consecutive days where the following 4 criteria are met for the mGCSI-DD:

Protocol CM4620-203 CONFIDENTIAL Page 17 of 31

- none for vomiting
- none or mild for nausea

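### Schedule footnote g (Protocol Appendix 8, repeated in SAP 3.2) tests each meal for any abdominal pain, while every definition of solid food tolerance tests for an increase in pain, so the primary endpoint could be recorded inconsistently between sites

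*Protocol*

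**What the plan says.** The primary endpoint is time to solid food tolerance. Protocol 5.2 defines a tolerated meal as at least half of the offered meal eaten "without an increase in abdominal pain or vomiting in the two hours after the meal". Protocol 10.7, which sets the analysis, says "solid meal without an increase in abdominal pain or vomiting in the two hours after completing the meal", and SAP 8.6.3 says "solid meal without an increase in abdominal pain or vomiting within the two hours of mealtime". The Protocol Synopsis, 3.1 and 5.3, and SAP 3.1 and 8.6.2, apply the same pain test. The time window is worded differently from place to place, but all eight places ask about an increase in pain.

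The recording instruction in Protocol 5.2 matches: staff note "if they either vomited or experienced an increase in abdominal pain in the two hours after the meal". The Synopsis, Protocol 3.1 and SAP 3.1 give the same instruction.

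Footnote g is attached to the Enhanced Recovery Strategy row of the Schedule of Events, which is the procedure that generates the endpoint. It has sites determine for each meal whether the patient "ate ≥50% of the meal without vomiting or having abdominal pain in the two hours after the meal". The schedule in SAP 3.2 repeats it: "without vomiting or having abdominal pain in the two hours after the meal". Neither document says which text governs when the schedule and the body differ.

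**The concern.** The two wordings are different tests. Pain that is present and unchanged passes one and fails the other. The plan expects such patients: abdominal pain is part of the diagnosis required for entry (Protocol 4.1), solid meals are offered from the end of the first infusion (5.2), and the discharge criteria accept pain that is controlled with medication (5.3).

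What is at stake is the per-meal source data for the primary endpoint. If a site notes only whether pain was present, an increase cannot be reconstructed later. The pain scale does not fill the gap, because it is scheduled by study assessment and not around meals. The same variable feeds the 48, 72 and 96 hour tolerance rates (SAP 8.7.1), time to medically indicated discharge (8.7.2) and the last tier of the composite (8.9). Sites are pooled (8.1.7) and the Cox model is stratified only by sex and organ-failure risk (8.6.1), so the analysis does not adjust for differences in recording between sites.

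**Working it through.** **1. The two rules side by side** (at least half of the solid meal eaten; two-hour window)

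| After the meal | Endpoint definition (Protocol 5.2, 10.7; SAP 8.6.3) | Footnote g |
|---|---|---|
| No pain, no vomiting | tolerated | passes |
| Pain present but unchanged, no vomiting | tolerated | fails |
| Pain increased | not tolerated | fails |
| Vomiting | not tolerated | fails |

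Only the second row differs. A patient with no pain cannot have had an increase, so meals that pass footnote g are a subset of meals that meet the definition. The first qualifying meal under the footnote is therefore the same meal or a later one. Recorded times are equal or later, and the rate at any fixed hour is equal or lower.

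**2. Compounding through SAP 8.6.3.** That section also requires that no later in-hospital meal shows an increase in pain or vomiting, with an exception for certain procedures. If unchanged pain at a later meal is recorded as a pain failure, an earlier meal that met the definition can be disqualified. The recorded time then moves by more than one meal.

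**3. The plan's own power figures** (Protocol 10.2; SAP 4), reproduced for context

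- 45% against 20%, 54 per group, two-sided 0.05, chi-squared without continuity correction: power 0.801. The stated 80% reproduces.
- Medians 72 and 144 h, exponential times, ratio 144/72 = 2.0: 86% power needs 4 × ((1.96 + 1.08) / ln 2)² = 77 events. The follow-up behind the 86% is not stated. With 54 per arm, expected events by T hours are 54(1 − 2^(−T/72)) + 54(1 − 2^(−T/144)). T = 192 h gives 78.1 events, and power Φ(√(78.1/4) × ln 2 − 1.96) = 0.865.

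**4. Effect of a common delay.** Assume, for illustration, that the footnote delays every patient by 24 h. The ordering of times is unchanged, so the hazard ratio stays 2.0 and only events pushed past the end of follow-up are lost. Follow-up of 192 h then behaves like 168 h: 73.2 events, power 0.843 against 0.865. Follow-up of 720 h behaves like 696 h: 106.0 events against 106.3, power 0.946 against 0.947.

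**5. Effect on the 72-hour rate**, under an assumed equal relative loss of responders in both arms (54 per arm, two-sided 0.05)

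| Assumed loss | Auxora vs placebo | Power |
|---|---|---|
| 0% | 45% vs 20% | 0.80 |
| 10% | 40.5% vs 18% | 0.74 |
| 20% | 36% vs 16% | 0.66 |
| 30% | 31.5% vs 14% | 0.59 |
| 40% | 27% vs 12% | 0.50 |

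Nothing in the documents selects a row. They do not say how many patients have unchanged pain when they first eat half a solid meal, or how many sites would work from the footnote.

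**The case against.** The strongest reply is that sites are sent to the right text. Protocol 8.4 ties the start of the feeding strategy to Section 5.2, and 8.5 to 8.8 each carry the instruction "Determine if, and when the patient tolerated solid food in the previous 24 hours (see Section 5.2", closing the bracket there. Section 8.12.9 also refers to 5.2 for the assessment procedure. Footnote g does not itself define tolerance, and the SAP copy reproduces a schedule and is not an analysis rule; the analysis follows SAP 8.6.3. The eCRF meal form is not in the documents and may already ask about an increase.

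Most of this stands, and it limits the point to a risk of inconsistent recording. It does not remove the conflict. The footnote is a per-meal instruction to sites, no precedence rule is given, and the cross-reference to 5.2 is absent from 8.9 (Days 12 to 28) and 8.10 (Day 30). An analysis rule about an increase also cannot be applied to data that record only the presence of pain.

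A reader might infer more than this. One tempting step is to add 24 h to both medians, giving 96 and 168 h, take the ratio 168/96 = 1.75, and conclude that power falls from 86% to Φ(√(77/4) × ln 1.75 − 1.96) = 0.69. That does not follow: it refits exponential curves to the shifted medians, whereas a common delay preserves the ordering and the hazard ratio (step 4). The 24 h is not in the documents either. The calculation also concerns a pairwise log-rank test, which is supplementary in SAP 8.6.5; the SAP's primary test is the gMCP-Mod contrast test at one-sided 15% (8.6.1).

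A reader might also infer that the hazard ratio must be diluted, or that unchanged pain is common. Neither is shown. Delays that vary between patients could add noise, but a treatment that reduced residual pain could make the contrast wider under the stricter rule. Assignment is randomised and blinded, and the documents give no evidence of bias between arms.

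**Conclusion.** The point holds as a current internal inconsistency in the recording of the primary endpoint. The direction is certain by logic: where the footnote is followed in place of Section 5.2, recorded tolerance times are equal to or later than those defined. The size is not known. It depends on three things the documents do not give: how many sites use the footnote, how often pain is present but unchanged after a qualifying meal, and what the eCRF asks. No effect on the hazard ratio or on the stated 86% power can be derived. The 72-hour table in step 5 rests wholly on its assumed loss and is not an estimate. The case for acting rests on having one recording rule for the primary endpoint and on the fact that the lost information cannot be recovered later.

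**What to change.** Reconcile footnote g in Protocol Appendix 8 and in SAP 3.2 with the endpoint definition in Protocol 5.2 and SAP 8.6.3, so that it asks about vomiting or an increase in abdominal pain in the two hours after the meal. Send sites a short clarification that tolerance is judged by Section 5.2. Confirm that the eCRF meal form captures an increase in pain and not only its presence. If meals have already been recorded on a presence-of-pain basis, identify the sites concerned before database lock. The cost is one phrase in each document, one site communication and one check of the form. The endpoint, sample size and analysis do not change.

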TEAE Treatment-emergent adverse event

TFLs Tables, figures and listings
ULN Upper limit of normal
WHO World health organization

1. INTRODUCTION

This statistical analysis plan (SAP) is based on the CM4620-203 Protocol version 4 dated 05 October 2023. The plan covers statistical analysis, tabulations and listings of safety and efficacy data to assess the safety and efficacy of Auxora compared to placebo in patients with acute pancreatitis and accompanying systemic inflammatory response syndrome (CARPO).

The statistical analyses and production of the outputs described in the SAP will be conducted and quality control (QC) reviewed, using SAS version 9.4 or higher.

2. STUDY OBJECTIVES

2.1 Primary Objectives:

- To assess the dose response and efficacy of three different dose levels of Auxora in patients with acute pancreatitis and accompanying SIRS;
- To assess the time to medically indicated discharge in patients who are responders to early tolerance of solid food intake versus non-responders.

2.2 Secondary Objective:

• To assess the safety and tolerability of varying doses of Auxora in patients with acute pancreatitis and accompanying SIRS

3. STUDY DESIGN

3.1 Overall Study Design

This double blind, randomized, placebo-controlled study will evaluate the efficacy, safety, and tolerability of three different dose levels of Auxora in patients with acute pancreatitis and accompanying SIRS.

Approximately 216 patients will be randomized 1:1:1:1 into one of 4 groups using a computer generated randomization scheme accessed through an interactive voice/web response system (IXRS). Randomization will be first stratified by sex (male or female) and then by risk for organ failure in the sex subgroups (higher or lower). Higher risk for organ failure is defined by the presence of both an elevated hematocrit (HCT \geq 44% for men or \geq 40% for women) and hypoxemia (imputed PaO₂/FiO₂ \leq 360). Lower risk for organ failure is defined by the absence of either or both an elevated hematocrit and hypoxemia. The PaO₂/FiO₂ will be determined using an arterial blood gas or imputed using pulse oximetry.

All patients will have received a Screening CECT/MRI of the abdomen/pancreas before being randomized into the study. CECTs/MRIs performed as standard of care may be used as the Screening CECT/MRI but must have been performed in the 24 hours before Consent or after Consent and before Randomization.

The Start of First Infusion of Study Drug (SFISD) should occur within 8 hours of the patient or LAR providing informed consent. Patients randomized to Group 1 will receive 2.0 mg/kg (1.25 mL/kg) of Auxora intravenously every 24 hours (±1 hour) for a total of three doses. Patients

Protocol CM4620-203 CONFIDENTIAL Page 6 of 31

randomized to Group 2 will receive 1.0 mg/kg (0.625 mL/kg) of Auxora intravenously every 24 hours (±1 hour) for a total of three doses. Patients randomized to Group 3 will receive 0.5 mg/kg (0.3125 mL/kg) of Auxora intravenously every 24 hours (±1 hour) for a total of three doses. Patients randomized to Group 4 will receive emulsion without any active pharmaceutical ingredient (placebo). Patients in Group 4 will receive one of three randomly assigned dose volumes, 1.25 mL/kg, 0.625 mL/kg, or 0.3125 mL/kg, which will be administered intravenously every 24 hours (±1 hour) for a total of three doses. The dosing will be based on actual body weight obtained at the time of hospitalization or screening for the study. As described in the pharmacy manual, the upper limit of the volume of Auxora and volume of placebo that will be administered will be 156.25 mL. The sponsor, investigators and patients will be blinded to the assigned group. In the event of a medical emergency, investigators will be able to receive the treatment assignment if required to provide optimal care of the patient.

For all 4 groups, a study physician or appropriately trained delegate will perform assessments at screening, at the baseline assessment, immediately prior to the SFISD, and then every 24 hours until 240 hours after the SFISD, or until discharge if earlier. If patients remain hospitalized at Day 12, assessments will then be performed every 48 hours starting on Day 12 until Day 28, or until discharge if earlier. Patients discharged from the hospital before Day 25 will return at Day 30 (+5 days) to perform the Day 30 assessments. If patients are discharged on Days 25-29, the Day 30 assessments may be performed prior to discharge.

Patients will receive another CECT of the abdomen/pancreas at the Day 30 (±5 days) visit. All CECTs performed as standard of care after randomization and before the Day 30 CECT will also be captured. A blinded central reader will read the Screening, Day 30, and any standard of care CECTs obtained between randomization and 30 days.

Patients will complete the modified American Neurogastroenterology and Motility Society Gastrointestinal Cardinal Symptom Index Daily Diary (mGCSI-DD) worksheet at the baseline assessment, at 96 hours, 168 hours, Day 14 and Day 21 (for patients who remain hospitalized on these days), on the day of discharge, and daily at bedtime after discharge until the Day 30 visit. Patients who are discharged on Days 25-29 will not complete the mGCSI worksheet after discharge.

It is recommended that all patients randomized in the study should receive care consistent with the 2018 American Gastroenterological Association (AGA) Institute Technical Review of the Initial Medical Management of Acute Pancreatitis. Patients should receive local standard of care (SOC) for the management of other medical conditions.

In patients with acute pancreatitis, the AGA strongly recommends early oral feeding (within 24 hours) rather than keeping the patient nil per mouth (Nil per Os, NPO). Patients randomized into the study, therefore, will be offered a low fat, ≥500-calorie solid meal at each mealtime after the infusion of the first dose of study drug if alert and not on mechanical ventilation. If the patient does not wish to eat the solid meal when offered or is unable to tolerate the solid meal, they should then be offered a liquid meal. The same approach should occur at each subsequent mealtime. When patients eat a solid meal, it should be recorded if they ate ≥50% of the meal and

Protocol CM4620-203 CONFIDENTIAL Page 7 of 31

if they either vomited or experienced an increase in abdominal pain in the two hours after eating a meal.

It is also recommended that all patients randomized in the study should not be discharged from the hospital until solid food is tolerated, abdominal pain has resolved or been adequately controlled, and there is no clinical evidence of infection. Tolerating solid food is defined as eating ≥50% of a low fat, ≥500-calorie solid meal without an increase in abdominal pain or vomiting. If the patient is not tolerating either solid or liquid meals, tube feedings should be considered.

All protocol required laboratory testing, except biomarker and PK samples, will be performed at the local laboratory. Results from the biomarkers and PK blood samples collected as part of the protocol and being tested at a central lab will not be available to assist the PI or treating physician in managing the patient.

